**Homocysteine in bariatric patients following laparoscopic roux-en-Y
gastric bypass surgery
Department of surgery
Medical university of Vienna
An exploratory study in 708 consecutive patients.**

EK1143/2013

[name]

Associate professor [name]

Department of surgery (head of department: Univ. [name], MD),
Medical University of Vienna

Translation of the original study protocol document approved by the local ethics
committee in 2014.

Table of content

1	Background	3
2	Outcome	3
3	Patients	4
4	Parameters	4
4.1	Primary outcome	4
4.2	Secondary outcomes	4
5	Methods	4
6	Statistics	5
7	Data privacy protection	5
8	Risk-benefit analysis	6
9	References	6

1 Background

Hyperhomocysteinaemia defined as serum levels above 15 $\mu\text{mol/l}$ is associated with numerous risks. There is an elevated risk in suffering from cardiovascular events (myocardial infarction, stroke, acute limb ischemia, deep veinous thrombosis) who are today's number one cause of death in the industrialized world (1). Furthermore, Homocysteine was found to be a mediator in dementia, Alzheimer's disease (2), osteoporosis induced pathological fractures (3) and diabetic retinopathia (4). The role of homocysteine in metabolic diseases is indisputable. Obesity is also associated closely with cardiovascular disease events, therefore it is necessary to provide a systematically analysis of changes in homocysteine levels following weight loss surgery.

Changes in homocysteine levels following bariatric surgery remain controversially discussed. Where some authors found postoperatively lower values (5, 6), others reported elevated values (7-10). Even some found no difference at all between preoperative and postoperative values of homocysteine (11-13). Some of these studies used outdated bariatric surgery procedures (7, 9, 13).

In literature the postoperative changes of homocysteine after bariatric surgery remain unrevealed. Therefore, we designed this survey to assess timeline changes of homocysteine with a long-time and high follow-up. This could be of importance to postoperative prophylaxis of cardiovascular disease events.

For homocysteine being only a surrogate parameter for cardiovascular events, we decided to reveal changes in homocysteine being of clinical relevance via assessing the actual cardiovascular disease events (stroke, myocardial infarction, deep veinous thrombosis, ...).

2 Outcome

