The primary outcome is to assess timeline changes of the peri and postoperative values of homocysteine in $\mu\text{mol/l}$ via the CMIA (chemiluminescent microparticle immunoassay) through study completion. Secondary outcomes include

demographic parameters like weight, height, folate, and vitamin B12. Furthermore, for determining clinical relevance we assessed the postoperative newly-onset number of cardiovascular events.

3 Patients

All patients received laparoscopic roux-en-Y gastric bypass at the department of surgery at the medical university of vienna over a six year period. All patients met the criteria for bariatric surgery: BMI of above 40 kg/m^2 without comorbidities or BMI of above 35 kg/m^2 with comorbidities including diabetes mellitus, arterial hypertension, hyperlipidaemia, obstructive sleep apnea syndrome, arthrosis and others. Minimal age was 18 years and highest age was 75 years for inclusion. Both female and male participants were eligible.

4 Parameters

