4.2 Secondary outcomes

Secondary outcome measurements include folate, vitamin B12 being well known to have impact on homocysteine metabolism. Furthermore, all standard laboratory parameters and demographic data will be assessed also. The postoperative incidence of newly-onset cardiovascular disease events will be reported.

5 Methods

Retrospective analysis of existing records of the department of surgery, medical university of vienna will be performed. To extract laboratory values out of the database the Archimed software will be utilized.

To reveal clinical relevance of changes in homocysteine values we will perform postal screening utilizing a questionnaire in all 708 participants. In the same step the informed consent form will be sent to each patient and they will be questioned if they have experienced any cardiovascular disease event after surgery (see IC form and questionnaire). An encrypted form of these lists is only available to the principal investigator and the study nurses.

Finally, the data will be compared to two state wide databases (AKIM and Webokra) to verify cardiovascular events.

6 Statistics

Descriptives

Case number strategy: the number of participants include all patients undergoing roux-en-Y gastric bypass consecutively over a six year period. We expect 708 cases. For this study being only exploratory we forwent a formal Power analysis.

To reveal statistical relevant postoperative changes of homocysteine we performed paired t-tests between preoperatively. Pearson's or Spearman's Correlations will be performed to reveal the influence of folate and vitamin B12 on the homocysteine metabolism.

The results of the postal screening section will be evaluated descriptively and compared to general incidences of cardiovascular disease events.

7 Data privacy protection

All patients will be numbered continuously and anonymized for further evaluation. Only authorized personnel will be able to access original names and data.

Furthermore, data will be stored and evaluated on personal computers at the medical university of Vienna with restricted access.

8 Risk-benefit analysis

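### Comparing cardiovascular events with general-population incidence is confounded by severe obesity in an uncertain net direction, so it cannot show that homocysteine changes are clinically relevant.

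*Combined protocol and SAP*

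**What the plan says.** **Purpose.** Section 2 (Outcome) gives the reason for counting events: "for determining clinical relevance we assessed the postoperative newly-onset number of cardiovascular events". Section 5 (Methods) repeats it: "To reveal clinical relevance of changes in homocysteine values we will perform postal screening utilizing a questionnaire in all 708 participants".

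**Comparator.** Section 6 (Statistics) says the survey results will be "evaluated descriptively and compared to general incidences of cardiovascular disease events". It gives no source for the incidences, no standardisation and no other reference group.

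**Who is in the cohort.** Section 3 (Patients) admits patients by two routes. One rests on weight alone: "BMI of above 40 kg/m^2 without comorbidities". The other has a lower weight threshold and asks for a further condition from an open list: "BMI of above 35 kg/m^2 with comorbidities including diabetes mellitus, arterial hypertension, hyperlipidaemia, obstructive sleep apnea syndrome, arthrosis and others".

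**Background risk.** Section 1 (Background) states: "Obesity is also associated closely with cardiovascular disease events".

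**Ascertainment.** Under section 5, patients receive a questionnaire by post with the consent form, in which "they will be questioned if they have experienced any cardiovascular disease event after surgery". Two databases are then used to verify events.

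**Other analyses.** Section 6 plans paired t-tests on homocysteine, and correlations of folate and vitamin B12 with homocysteine. Neither relates homocysteine to cardiovascular events.

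**The concern.** The protocol names obesity as closely tied to the outcome, selects every patient on it, and then compares them with a population not selected on it. Standardising for age, sex and person-time would be worthwhile but would not remove this difference.

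The comparison carries the whole clinical-relevance question, because no analysis links a patient's homocysteine to that patient's events. A rate above the general figure could be read as harm from raised homocysteine when it only reflects obesity. A rate at or below it could be read as reassurance when weight loss or missed events have hidden a harm. The Background says the results could matter for postoperative cardiovascular prophylaxis, so either misreading could be carried forward.

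**Working it through.** The plan gives no figure to reproduce: 708 is a count of consecutive cases, and section 6 states that no formal power analysis was done. The calculations below are illustrations. Only 708 comes from the documents; event rates, follow-up, risk ratios and capture fractions are assumptions.

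**Step 1. What the ratio contains when homocysteine has no effect.**

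Observed/expected = (baseline risk relative to the general population) × (relative risk after surgery and weight loss) × (share of events captured).

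Assumed ranges: baseline 1 to 3, post-surgery 0.6 to 1.0, capture 40% to 100%.

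| Baseline | Post-surgery | Capture | Observed/expected | Would look like |
|---|---|---|---|---|
| 2 | 1.0 | 1.0 | 2.0 | excess |
| 2 | 0.6 | 0.8 | 0.96 | no difference |
| 2 | 1.0 | 0.4 | 0.80 | deficit |
| 1 | 0.6 | 0.4 | 0.24 | lowest in range |
| 3 | 1.0 | 1.0 | 3.0 | highest in range |

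**Step 2. Selection alone, with full capture and no benefit from surgery.**

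Expected events = 708 × 6 years × 3 per 1,000 = 12.7. If baseline risk is doubled, about 25 events are observed. Observed/expected = 25/12.74 = 1.96, exact Poisson 95% CI 1.27 to 2.90.

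The grid uses rates of 2, 3 and 5 per 1,000 person-years, 4 and 6 years of follow-up, and risk ratios of 1.5, 2 and 2.5. That is 3 × 2 × 3 = 18 scenarios:

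- Lower limits run from 0.61 to 1.87.
- The lower limit is below 1 in 6 of 18 scenarios: five of six at a ratio of 1.5, one of six at 2.0 and none at 2.5 (minimum 1.35).

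**Step 3. How often the count would look notable without any homocysteine effect.**

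An excess means a count in the upper 2.5% Poisson tail of the expected number; a deficit means one in the lower 2.5% tail. Expected events = 708 × 4 × 5 per 1,000 = 14.2, so an excess is 23 or more and a deficit is 6 or fewer.

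| True ratio from the factors in step 1 | Probability of excess | Probability of deficit |
|---|---|---|
| 0.5 | <1% | 44% |
| 1.5 | 38% | <1% |
| 2.0 | 86% | <1% |

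For rates of 2 to 10 per 1,000 and 4 to 8 years, a ratio of 2.0 gives an excess with probability 46% to more than 99%.

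**Step 4. Reading.** The first two steps show that the same absence of a homocysteine effect is compatible with results on either side of 1. The third shows that either can look convincing. The observed/expected ratio therefore does not identify a homocysteine effect.

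**The case against.** **This is a descriptive secondary outcome in an exploratory study.** True: no test or confidence interval is planned for the comparison, the protocol presents its results as a basis for further hypotheses, and it never says that an excess will be read as a homocysteine effect. This limits the weight of the point but does not remove it. Sections 2 and 5 assign the events the task of showing clinical relevance, and the only analysis offered cannot do so.

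**The size is assumed.** Also true. Choosing a risk ratio of 2 yields an observed/expected ratio near 2. The figures show what is possible, not what will happen.

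**A stronger reading is tempting: that an excess is built into the design.** The documents do not support it. Selection pushes the rate upward, but weight loss may lower risk, non-responders and patients who have died may be missed, and only new-onset events count. Whether the database check also finds events that nobody reported is not stated.

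**A reader might also infer that everyone enters with diabetes, hypertension or hyperlipidaemia.** Section 3 does not say that. The higher BMI route needs no comorbidity, and the lower one also accepts sleep apnoea, arthrosis and others. What all patients share is severe obesity.

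**An obese reference group would not cure the problem.** This stands. Comparing operated patients with unoperated obese people removes the obesity mismatch, but still mixes homocysteine with surgery and weight loss.

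**Conclusion.** The point holds in a limited form. The general-incidence comparison is confounded by obesity-related risk, its net direction is uncertain, and no result from it (excess, null or deficit) can support the clinical-relevance conclusion that sections 2 and 5 seek.

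That conclusion rests on the protocol's own text: the entry criteria, the Background statement on obesity, and the absence of any analysis relating homocysteine to events. The range of 0.24 to 3.0 and the tail probabilities rest on assumed inputs and only illustrate it.

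The change should be made, because following the plan as written invites a confounded conclusion and the correction is cheap.

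**What to change.** In section 6:

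1. State that the comparison with general incidences is descriptive context only and will not be interpreted, in either direction, as evidence on the clinical relevance of homocysteine changes. This is the essential part.
2. Address that question with a descriptive within-cohort analysis of events by homocysteine level or change, using values measured before the event. One natural split is above versus at or below 15 µmol/l, the threshold the Background uses to define hyperhomocysteinaemia. This needs event dates; the documents do not say whether the questionnaire or the databases supply them, so this should be confirmed.
3. Where available, add published incidences in unoperated severe obesity as a second reference, noting that the contrast still mixes homocysteine with surgery and weight loss.

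A table of comorbidities at surgery would help readers judge either reference, if they can be extracted; section 3 says patients met the criteria, not that each comorbidity was recorded in usable form.

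**Cost.** Wording, a literature reference and one further tabulation of homocysteine and event data already planned for collection; no new patients, visits or procedures. The downsides are real. Few events are likely (12.7 expected in the illustration above, before splitting by homocysteine), so within-cohort estimates will be imprecise, and they remain observational. Rates from obese populations are less locally matched than national figures.
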